### **Other Maternal Outcomes**

Calculate descriptive statistics for the following variables

- Weight
- BMI
- Daily Insulin Requirements (units) at the moment of the visit
- Microalbumin excretion with albumin/creatinine ratio
- Number of SMBG per subject per day (patient self-reported)  
per
- Pregnancy trimester
- Duration of treatment received

## ***7.10. Safety Evaluation***

All site reported adverse events for enrolled subjects will be summarized, including:

- Incidence of severe (clinical) hypoglycemia
- Incidence of DKA
- Serious adverse events (SAE)
- Unanticipated device effects (UADE)

This document is electronically controlled. Printed copies are considered uncontrolled.

**Confidential**

Detailed information of all adverse events will be provided in listings. The summary of adverse events will also be provided per trimester.

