**Confidential**

affects between 25-40% mothers and is three to five times as frequent in early pregnancy as in the period prior to pregnancy. Rates of SH in the late first and early second trimester showed an increase of 16%, and in an intensively treated group subjects had 15 times more SH than the conventionally treated group. Nocturnal hypoglycaemia is also common in the first trimester, with a 37% prevalence shown by hourly venous sampling between 22:00h-07:00h. Ironically, during pregnancy, hypoglycaemia is less harmful to the fetus than to the mother, but hyperglycaemia poses increased risks for the fetus. Therefore, from the perspective of fetal outcomes, strict metabolic control in early pregnancy must still be advocated, but other means for preventing severe hypoglycaemia should be implemented.

CSII in non-pregnant Type 1 subjects was associated with a reduced rate of severe hypoglycaemia without adversely affecting glycaemic control when compared with MDI therapy. There is recent convincing evidence from multicenter randomised controlled trials (RCT) that both CSII and continuous glucose monitoring (CGM) independently, or in combination as sensor-augmented pump therapy (SAP) improve glycaemic control by decreasing HbA1c in the range of -0.43% to -1.2%. An RCT of 71 pregnancies complicated with diabetes had an end-of-pregnancy improvement of -0.6% and reduced risk of macrosomia when using CGM.

Postprandial blood glucose levels have a stronger association with incidence of macrosomia than HbA1c. Two RCTs found that monitoring of post-prandial glucose levels produced better outcomes than pre-prandial monitoring. Neonatal outcomes are more closely associated with hyperglycaemic excursions than with the average glycaemic control. The frequency, magnitude and duration of hyperglycaemic excursions, are best captured by CGM which has an accuracy comparable to gold standard plasma glucose measurements in pregnancy yet provides continuous information on glucose levels. Indeed, analysis of CGM for hyperglycaemia may be a useful marker of anticipated neonatal outcomes.

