## **5. Investigation Plan**

### **Study design:**

The project is designed as a multi-center prospective observational Post-Market-Release study to be conducted in up to 30 centers in Poland.

Total duration of the study per patient will be up to 22 months (up to 12 months pre-conception phase, pregnancy, and 6 weeks after delivery). The optimal study start is the beginning of pre-conception phase, however, pregnant women up to the 16th week of pregnancy can participate in the study too. The study end is 6 weeks after delivery. If conception does not occur within 12-months, the patient's study participation is terminated, and the insulin pump might be taken away from the patient. The following therapy is decided by the investigator. If the pump is not taken away after the 12-month of trial period for conception, the patient can continue insulin pump therapy until the pump is needed for another patient.

The study started in May 2013; enrolment period is planned for 30 months which can be modified by the decision of the Steering Committee. The final report will be available within 24 months after the end of enrolment.. Data collection will be stopped when data have been collected from 100 pregnancies with complete follow-up (including pre-conception phase, pregnancy, delivery and 6 weeks of lactation).

This document is electronically controlled. Printed copies are considered uncontrolled.

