**Inclusion Criteria:**

A subject is eligible for the study if the following criteria are met:

1. Female diagnosed with Diabetes Mellitus Type 1
2. Subject indicated by HCP to start insulin pump therapy (CSII) or sensor augmented pump therapy (SAP) due to the desired or established pregnancy
3. HCP has prescribed the use of Orchestra donated device to the subject independently of the study
4. Signed Patient Informed Consent (PIC)
5. Subject is 18 to 45 years old, planning immediate pregnancy (within the next 12 months) or being pregnant within the first trimester until the 16th week of amenorrhea
6. Subject has been on MDI for at least 3 months before starting pump therapy

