### Maternal outcomes

- HbA1c (local laboratory) – last value before insulin pump therapy started (retrospective value from patient's medical file), 2-3 values during pregnancy, and one value at the end of the study.
- Proportion of women achieving HbA1c <6.0%, 6.5%, 7%, 7.5% and 8% at each trimester
- Serious adverse events
  - Severe hypoglycaemia (according to the standard definition requiring third party assistance – see point F 5. 1) from the period of 12 months prior to study start until study end
  - DKA from the period of 12 months prior to study start until study end
  - Miscarriage, hospitalization because of uterine bleeding, hospitalization because of instable glycaemia and others
  - Any hospital admission
- Weight, BMI
- Daily insulin use
- Medical information: Microalbumin excretion with albumin/creatinin ratio, blood pressure, parity, folic acid and any other supplementation, White classification, diabetes duration, previous insulin regimen
- Number of SMBG/day (patient self-reported)
- Patient questionnaires:
  - Hypoglycaemia Fear Survey (HFS) collected at enrollment, 2-3 x during pregnancy, and 6 weeks after delivery
  - Diabetes Treatment Satisfaction Questionnaire (DTSQs, status version), collected at enrollment, 2-3 x during pregnancy, and 6 weeks after delivery, and Diabetes Treatment Satisfaction Questionnaire (DTSQc, change version), collected at 24 weeks into pregnancy
- Device Data:
  - Descriptive statistics for SMBG and SG (mean, SD, median, min and max)
  - time spent SG < 50 mg/dL
  - time spent SG between 50-70 mg/dL

This document is electronically controlled. Printed copies are considered uncontrolled.

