#### **7.1.3. *Analysis Sets***

All enrolled subjects who have participated in Orchestra Pregnancy Observational Study in Poland will be included in the efficacy analysis population. All enrolled subjects will be included in the safety analysis population.

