### **7.6. *Demographic and Other Baseline Characteristics***

Baseline information and demographic characteristics such as age, gender, weight, BMI, diabetes duration, insulin regimen, etc. will be summarized. Medical information such as previous severe hypoglycemia and DKA history up to 12 month prior to study start will also be summarized.

This document is electronically controlled. Printed copies are considered uncontrolled.

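### A single incidence of severe hypoglycaemia and DKA, split only by trimester, depends on when women enrolled and gives pre-conception and postpartum events no stratum

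*SAP*

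**What the plan says.** SAP 7.10 lists "Incidence of severe (clinical) hypoglycemia", and likewise of DKA, among the safety summaries for enrolled subjects. The only breakdown over time is the sentence "The summary of adverse events will also be provided per trimester". Protocol H.1.2 (Safety Analysis) matches it. SAP 7.1.3 sets the population: "All enrolled subjects will be included in the safety analysis population". Nothing says whether incidence means women with an event or events per unit of time, and trimester boundaries are not given.

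The endpoint itself is wider than the trimesters. SAP section 5 (Maternal outcomes) collects severe hypoglycaemia "from the period of 12 months prior to study start until study end", and DKA over the same window. The part before study start appears only as a baseline characteristic in SAP 7.6: "Medical information such as previous severe hypoglycemia and DKA history up to 12 month prior to study start will also be summarized".

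Three other places matter:

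- On follow-up, SAP section 5 (Study design) says: "Total duration of the study per patient will be up to 22 months". It also admits women already pregnant, up to week 16.
- On natural course, the SAP introduction says that severe hypoglycaemia "is three to five times as frequent in early pregnancy as in the period prior to pregnancy".
- SAP 7.9 splits glycaemic, pregnancy, neonatal and other maternal outcomes by length of treatment, and names four enrolment and conception groups for the primary objectives. SAP 7.10 carries over neither device.

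**The concern.** Three kinds of women are pooled: those followed from before conception to six weeks postpartum, those who enter already pregnant, and those who never conceive. They are observed for very different lengths of time and in different physiological states. A simple proportion with an event will vary with length of follow-up. A rate pooled over phases will vary with the share of time spent in early pregnancy. Both depend on when women enrolled.

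The trimester split does not solve this. A woman who never conceives has no trimester, and neither does pre-conception or postpartum pump time. A woman who enters at week 10 contributes only the end of trimester 1, so even a trimester-1 figure without time at risk is not comparable between the two enrolment routes.

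The stake is interpretation. Protocol J.1 anticipates that sensor-augmented pump therapy will help prevent severe hypoglycaemic events. The report will contain both a 12-month history and an on-study incidence, and readers are likely to set them side by side.

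**Working it through.** **Inputs from the documents.** Up to 12 months pre-conception, then pregnancy, then 6 weeks; latest entry at week 16; early-pregnancy multiplier 3 to 5 (SAP introduction); planned groups of 100 complete, 300 enrolled pregnant and 100 early terminations (SAP section 6).

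**Assumptions.** Delivery at week 40 of amenorrhoea and conception at week 2; base rate 0.1 to 0.5 events per woman-year, with 0.3 as the example; multiplier 0.5 to 1.0 after the early peak, including postpartum; no pump effect.

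**Step 1: the plan's own figure.** 12 months + (38 + 6) weeks ÷ 4.348 weeks per month = 22.1 months, which reproduces the stated 22. In weeks, 52 + 14 + 24 + 6 = 96. Entry at week 16 gives 24 + 6 = 30 weeks, or 6.9 months. The spread is 22.1 ÷ 6.9 = 3.2-fold.

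**Step 2: follow-up alone.** P(at least one event) = 1 − exp(−rate × years).

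| Rate per woman-year | 6.9 months | 22.1 months | Ratio |
|---|---|---|---|
| 0.1 | 5.6% | 16.8% | 3.0 |
| 0.3 | 15.8% | 42.5% | 2.7 |
| 0.5 | 25.0% | 60.2% | 2.4 |

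**Step 3: phase mix, after allowing for time.** For complete follow-up with 12 months pre-conception, in weeks at the non-pregnant rate:

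- Peak to week 16 (14 weeks). Low: 52 + 14×3 + 30×0.5 = 109; 109 ÷ 96 = 1.14. High: 52 + 14×5 + 30×1.0 = 152; 152 ÷ 96 = 1.58.
- Peak to week 12 only (10 weeks), then 1.16 for four weeks. This reads the introduction's 16% increase around the end of the first trimester as relative to the non-pregnant rate; the text leaves its reference period unclear. Low: 52 + 30 + 4.64 + 15 = 101.64; ÷ 96 = 1.06. High: 52 + 50 + 4.64 + 30 = 136.64; ÷ 96 = 1.42.

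The range is therefore 1.06 to 1.58. On the same footing, a woman who never conceives has 1.0, and a week-16 entrant has 0.5 to 1.0.

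**Step 4: what the history contains.** For a week-16 entrant, the 12 months before study start include about 14 weeks of early pregnancy. With the peak run to week 16, her history is worth 38 + 14×(3 to 5) = 80 to 108 weeks at the non-pregnant rate. Her on-study events are worth 15 to 30 weeks. The event ratio is 15/108 to 30/80 = 0.14 to 0.38. The rate ratio is 0.5 ÷ (108/52) to 1.0 ÷ (80/52) = 0.24 to 0.65. With no pump effect, this would look like a large benefit.

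**Step 5: time outside any trimester.** For complete follow-up with 12 months pre-conception, (52 + 6) ÷ 96 = 60%; with 6 months it is 46%. Across the planned cohort it is about 37% to 50%, assuming 6 to 12 months pre-conception, pregnant entry at week 10, and 50 to 100 of the early terminations being 12-month non-conceivers.

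**Step 6: precision of a pre-conception rate beside the history.** The 95% limits are the rate ratio divided and multiplied by exp(1.96 × √(1/E₀ + 1/E₁)), where E₀ and E₁ are the events in the history and on study. With 100 women, 6 months and 0.1 per woman-year, E₀ = 10 and E₁ = 5, and the factor is 2.9. With 200 women, 9 months and 0.5, E₀ = 100 and E₁ = 75, and the factor is 1.35. This ignores pairing and overdispersion.

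**The case against.** The study is descriptive, severe hypoglycaemia is outside the primary objective, and no comparison of on-study events with the history is planned. All adverse events will be listed, and protocol F.6.2 puts the onset date on the event form. So no information is missing. This stands, and it limits the point to how the summary is specified.

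The appendix table shells are not visible, so a phase column cannot be excluded. The version history names summary tables of serious adverse events without a phase or enrolment split in their titles, while some other tables have one. That is suggestive only. The SAP text as written still specifies neither time at risk nor the two missing strata.

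A reader might infer that the plan discards a clean pump-versus-injection comparison, because pre-conception pump time and the history are both non-pregnant. The documents do not support that, for these reasons:

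- The injection requirement covers only part of the history window: "Subject has been on MDI for at least 3 months before starting pump therapy".
- The history is a retrospective count, while on-study events are prospective reports.
- Women preparing for pregnancy are likely to be seeking tighter control, and the introduction itself links better HbA1c with more hypoglycaemia.
- The six postpartum weeks are also non-pregnant pump time.
- About two thirds of women receive a stand-alone pump, so the contrast would not test the sensor-related benefit in J.1.

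A reader might also infer that the pooled figure must look worse than the history. It need not. Take 300 week-16 entrants, 100 with complete follow-up and 100 non-conceivers followed for 12 months, with the peak to week 16. Pooled events would then be about 0.55 to 0.77 times the pooled histories with no pump effect. The direction depends on the enrolment mix.

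**Conclusion.** The concern holds as a weakness in the planned safety summary. Unequal follow-up alone can move the proportion of women with an event from about 16% to about 42% at an assumed 0.3 per woman-year. Rates per woman-year cure that, but a rate pooled over phases still sits at about 1.06 to 1.58 times the non-pregnant rate for complete follow-up with no pump effect. That range rests on the documents' three- to fivefold multiplier, the assumed length of the peak and the assumed later multiplier of 0.5 to 1.0. The multiplier concerns severe hypoglycaemia; for DKA only the follow-up argument is quantified here. Pre-conception and postpartum events fall within the endpoint but have no stratum.

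None of this shows that the sponsor intends a before-after claim, or that a valid one is available. The change lies between worth considering and advisable: it is cheap and makes the safety figures interpretable.

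**What to change.** In SAP 7.10, and in protocol H.1.2 to match:

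1. Report severe hypoglycaemia and DKA as events per woman-year, and as the number of women with at least one event together with time at risk.
2. Give both in five phases: pre-conception on pump, trimesters 1, 2 and 3, and delivery to six weeks. Define the trimester boundaries, and split by enrolment before or during pregnancy.
3. For women enrolled before conception, the pre-conception rate may be tabulated beside their 12-month history as description only. Note that the history is retrospective, that only three months of injection therapy are guaranteed, and that precision is low.
4. State that pooled on-study or pregnancy-phase figures are not to be read against the 12-month history as a pump effect, and that for women enrolled while pregnant this history already includes early pregnancy.

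No new data are needed. Onset dates are on the event form, pregnancy start is a data-collection time point, and delivery date and weeks of pregnancy are recorded (protocol F.3). The cost is SAP wording, some extra table work, and small strata with imprecise rates.

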### **7.11. Health Outcomes Analyses**

Not Applicable

### **7.12. Changes to Planned Analysis**

Not Applicable

## **8. Validation Requirements**

Level I validation is required for Statistical and SAS programming of primary endpoint. Level I requires that the peer reviewer independently programs output and then compares the output with that generated by the original Statistical Programmer.

**Confidential**

[figure not shown]
This document is electronically controlled. Printed copies are considered uncontrolled.

**Confidential**

[figure not shown]
This document is electronically controlled. Printed copies are considered uncontrolled.

**Confidential**

This document is electronically controlled. Printed copies are considered uncontrolled.

[figure not shown]
**Confidential**

This document is electronically controlled. Printed copies are considered uncontrolled.

[figure not shown]
**Confidential**

[figure not shown]
This document is electronically controlled. Printed copies are considered uncontrolled.

**Confidential**

[figure not shown]
This document is electronically controlled. Printed copies are considered uncontrolled.

**Confidential**

[figure not shown]
This document is electronically controlled. Printed copies are considered uncontrolled.

**Confidential**

[figure not shown]
This document is electronically controlled. Printed copies are considered uncontrolled.

**Confidential**

[figure not shown]
This document is electronically controlled. Printed copies are considered uncontrolled.

**Confidential**

[figure not shown]
This document is electronically controlled. Printed copies are considered uncontrolled.

**Confidential**

This document is electronically controlled. Printed copies are considered uncontrolled.

[figure not shown]
**Confidential**

This document is electronically controlled. Printed copies are considered uncontrolled.

[figure not shown]
**Confidential**

[figure not shown]
This document is electronically controlled. Printed copies are considered uncontrolled.

**Confidential**

[figure not shown]
This document is electronically controlled. Printed copies are considered uncontrolled.

**Confidential**

[figure not shown]
This document is electronically controlled. Printed copies are considered uncontrolled.

**Confidential**

[figure not shown]
This document is electronically controlled. Printed copies are considered uncontrolled.

**Confidential**

This document is electronically controlled. Printed copies are considered uncontrolled.

[figure not shown]
**Confidential**

This document is electronically controlled. Printed copies are considered uncontrolled.

[figure not shown]
**Confidential**

**Table X. Neonatal Data after Six Weeks (Overall)**

This document is electronically controlled. Printed copies are considered uncontrolled.

[figure not shown]
**Confidential**

This document is electronically controlled. Printed copies are considered uncontrolled.

[figure not shown]
**Confidential**

[figure not shown]
This document is electronically controlled. Printed copies are considered uncontrolled.

**Confidential**

[figure not shown]
This document is electronically controlled. Printed copies are considered uncontrolled.

**Confidential**

[figure not shown]
This document is electronically controlled. Printed copies are considered uncontrolled.

**Confidential**

[figure not shown]
This document is electronically controlled. Printed copies are considered uncontrolled.

**Confidential**

[figure not shown]

This document is electronically controlled. Printed copies are considered uncontrolled.

**Confidential**

[figure not shown]

**Confidential**

This document is electronically controlled. Printed copies are considered uncontrolled.

[figure not shown]
**Confidential**

This document is electronically controlled. Printed copies are considered uncontrolled.

[figure not shown]
**Confidential**

[figure not shown]
This document is electronically controlled. Printed copies are considered uncontrolled.

**Confidential**

[figure not shown]
This document is electronically controlled. Printed copies are considered uncontrolled.

**Confidential**

[figure not shown]
This document is electronically controlled. Printed copies are considered uncontrolled.

**Confidential**

[figure not shown]
This document is electronically controlled. Printed copies are considered uncontrolled.

**Confidential**

[figure not shown]
This document is electronically controlled. Printed copies are considered uncontrolled.

**Confidential**

[figure not shown]
This document is electronically controlled. Printed copies are considered uncontrolled.

**Confidential**

This document is electronically controlled. Printed copies are considered uncontrolled.

[figure not shown]
**Confidential**

This document is electronically controlled. Printed copies are considered uncontrolled.

[figure not shown]
**Confidential**

[figure not shown]
This document is electronically controlled. Printed copies are considered uncontrolled.

**Confidential**

[figure not shown]
This document is electronically controlled. Printed copies are considered uncontrolled.

**Confidential**

[figure not shown]
This document is electronically controlled. Printed copies are considered uncontrolled.

**Confidential**

[figure not shown]
This document is electronically controlled. Printed copies are considered uncontrolled.

**Confidential**

This document is electronically controlled. Printed copies are considered uncontrolled.

**Confidential**

This document is electronically controlled. Printed copies are considered uncontrolled.

**Confidential**
